8.4 Missing Data

No imputation method will be implemented for any missing items. The planned outcomes research analyses will be based on all available data points collected during the course of the study.

For the EORTC QLQ-C30, values will be imputed for missing items by using values equal to the average of the non-missing items for any scale in which at least half the items are completed. A scale in which fewer than half of the items are completed will be treated as missing.

Once instrument data are scored, no imputation will be used to handle missing data. In the longitudinal model, imputing missing data may lead to underestimating the variance of treatment effects over time and unintentional biasing of estimates. Once the type and source of missing data observed is evaluated (e.g., missing at random [MAR], missing completely at random [MCAR], missing not at random [MNAR]), appropriate measure will be taken to handle missing data. Recommended statistical approaches to handling missing data particularly for longitudinal studies involve generalized linear mixed models when the data are MAR or MCAR. Realistically, since one cannot rule out MNAR in clinical trial longitudinal data, a pattern mixture model will be employed to investigate the possibility of MNAR. Mixed models are seen as an unbiased estimate under MAR conditions, and pattern mixture models are a method for identifying missing data as MAR or MNAR, as well as meaning behind the missing data. If the worst case analysis provides similar results to the model with no missing data imputed, then the results from the original model are likely robust to missing data.

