8.4.6 Outcomes Research Analyses

The patients' self-report of their quality of life at baseline and change in their QoL in subsequent visits as recorded in the EORTC QLQ-C30 and EQ-5D-3L questionnaires will be summarized at each time point for the full safety analysis set. In addition, EORTC QLQ-C30 mean domain score and mean change from baseline in domain score will be reported. The overall global health score and domain score (functional and symptom score) for each patient will be calculated using the EORTC QLQ-C30 scoring algorithm. A mixed effects random model may be fitted for the mean change from baseline with time as the main factor and patient level characteristics like age, sex, Performance Status, and other patient characteristics as covariates.

Additionally, the EQ-5D-3L assessment will be performed. The EQ-5D-3L comprises 5 dimensions (mobility, self-care, usual activities, pain/discomfort and anxiety) and a visual analog rating scale). The responses to the EQ-5D-3L domains will be converted to health status index based on the European scoring algorithm.

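### SAP 8.4 bases the handling of missing quality-of-life data on a MAR/MNAR classification that observed data cannot supply, with or without a pattern mixture model

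*SAP*

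**What the plan says.** SAP 8.4 sets an order. First the mechanism is assessed: "Once the type and source of missing data observed is evaluated" (MAR, MCAR and MNAR are given as the possible answers), "appropriate measure will be taken to handle missing data". The measure is not named, but the section recommends "generalized linear mixed models when the data are MAR or MCAR".

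It then grants that MNAR cannot be excluded in this kind of data, and for that reason commits to a further model: "a pattern mixture model will be employed to investigate the possibility of MNAR". The next sentence gives that model its role: "pattern mixture models are a method for identifying missing data as MAR or MNAR, as well as meaning behind the missing data".

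The section closes with a robustness rule: "If the worst case analysis provides similar results to the model with no missing data imputed, then the results from the original model are" probably robust. Neither the worst case nor the degree of similarity is defined. Nor are the dropout patterns, the identifying restrictions, any test or any threshold. The same section also rules out imputation once the instruments have been scored.

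The only longitudinal model is in protocol 8.4.6, and it is optional: "A mixed effects random model may be fitted for the mean change from baseline with time as the main factor". The visible text of SAP 7.8.1 and 7.8.2 lists descriptive summaries only.

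**The concern.** The distinction between MAR and MNAR lies wholly in the scores after dropout, which are not in the database. A step that reads the mechanism off the data and then selects the method therefore asks the data for something they do not contain. It also moves the choice of method to after the data have been seen.

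Informative dropout is plausible here. Protocol Table 5.1-2 schedules the QLQ-C30 on treatment. Protocol Table 5.1-3 carries only the EQ-5D-3L into follow-up, and SAP Table 3 agrees. Treatment stops for, among other reasons, toxicity and progression without clinical benefit (protocol 3.5 and 4.6.4), so QLQ-C30 scores may well cease when patients are doing worse.

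What is at stake is the reading of the quality-of-life results. A mean change could be called robust when it is too favourable by several points, or an unbiased MAR analysis could be set aside.

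**Working it through.** The plan gives no figure on this point, so there is none to reproduce. The check is one logical step, one line of arithmetic and a simulation.

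**1. What can be identified.** For a patient with dropout pattern r, the joint density is f(r) × f(observed scores | r) × f(unseen scores | observed scores, r). Data inform the first two factors only. MAR is a statement about the third: unseen scores follow the same conditional distribution as in patients still being observed. Subtract 10 points from every unseen score and the third factor changes (MAR becomes MNAR), but the first two do not. Any test computed from recorded scores therefore behaves identically in the two cases. This holds whichever test is chosen.

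**2. Size of the error when such a shift is missed.** Bias of the MAR mean at the last visit = proportion dropped out × shift. With the SAP 7.8.1 important difference of 10 points:
- 30% dropout (assumed): 0.30 × 10 = 3.0 points
- 60% dropout (assumed): 0.60 × 10 = 6.0 points

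A dropout log-odds of -1.8 per occasion (assumed) is a hazard of 0.142. SAP 7.8 requires at least one post-baseline assessment, which leaves three dropout occasions over five visits: 1 - 0.858³ = 36.8%. The bias is then 0.368 × 10 = 3.7 points, or 0.368 × 15 = 5.5 points for a 15-point fall. Counting dropout straight after baseline as a fourth occasion would give 45.8%, with 4.6 and 6.9 points, but those patients are outside the SAP's analysis set.

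**3. What the usual comparison detects.** Inputs from the documents: five visits (Weeks 1, 5, 9, 13 and 17, from the 4-weekly schedule in protocol Table 5.1-2); dropout only after the first post-baseline visit (SAP 7.8); n = 160, 640 and 800 (protocol 8). Assumed inputs: SD 25; correlation 0.3 or 0.6; cumulative dropout 30% or 60%; log-odds 0.7 per SD where dropout depends on a score. The pattern mixture fit compared dropouts with completers, tested at 5% either jointly (pattern and pattern × time, 2 df) or as pattern × time alone (1 df). There were 400 runs per cell, so the Monte Carlo standard error at 5% is √(0.05 × 0.95 / 400) = 1.1 percentage points. Ranges are over all assumed settings.

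| True mechanism | Joint test significant | Pattern × time significant | Bias of MAR mixed model (points) |
|---|---|---|---|
| MCAR | 4-8% | 3-7% | about 0 |
| Dropout unrelated to recorded scores, unseen 10-point fall (MNAR) | 4-6% | 3-7% | about 3 (30% dropout), 6 (60%) |
| MAR: dropout depends on last recorded score | 93-99% (n=160), 100% (n=640-800) | 28-44%, 78-97% | at most 0.05 |
| As MAR row, plus unseen 10-point fall (MNAR) | 91-99%, 100% | 28-42%, 79-98% | 2.9-3.0 (30%), 5.7-5.9 (60%) |
| MNAR driven by the part of the current score not predicted by earlier ones | 4-7% | 3-6% | 1.9-5.2 |
| MNAR driven by the whole current score | 30-91%, 87-100% | 5-17% (all n) | 1.3-4.6 |

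Rows 1 and 2 have the same rejection rates up to simulation error, as do rows 3 and 4, although one of each pair is unbiased and the other is not. Row 3 shows valid MAR data being flagged. Rows 2 and 5 show MNAR passing at about the nominal rate. Row 6 shows MNAR that the joint test often catches.

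**4. Dependence on the inputs.** How often MAR is flagged depends on how strongly dropout follows the last score. Above, that was 0.7/25 = 0.028 log-odds per point. A second simulation (3,000 runs; random intercept SD 15, slope SD 2 per visit, residual SD 12) also allowed dropout straight after baseline. Pattern × time was significant in 13.1% (N=160) and 37.1% (N=640) at 0.02 per point, and in 34.3% and 89.5% at 0.04 per point.

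**The case against.** The strongest reply is that SAP 8.4 never specifies the comparison tested above. It defines no pattern grouping, contrast or threshold, and ties no action to a pattern mixture p-value. A pattern mixture model with stated identifying restrictions or shifts would also satisfy the text and is a sound sensitivity analysis. The section itself grants that MNAR cannot be excluded, and its robustness statement rests on the worst-case comparison. This stands in part: the MCAR-type null describes common practice, not the SAP's wording. It does not rescue the clause on identification, which fails for any test, nor the step that evaluates the mechanism before selecting the handling.

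Three stronger readings are tempting and unsupported.
- **That the scheme always passes MNAR as harmless.** Row 6 shows otherwise; "can miss" would be the right strength, not more.
- **That a MAR/MNAR label alone decides whether the mixed model is believed.** The section says only that an unnamed measure follows the evaluation.
- **That the quality-of-life results would be badly biased.** The biases found are below the SAP's 10-point important difference and rest on assumed variances, dropout and shifts.

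The consequence is also limited. Quality of life is not a listed primary or secondary endpoint, the visible SAP analyses are descriptive, the mixed model is optional, and the trial has one arm. Parts of the SAP's endpoint and outcomes sections are redacted, so further model detail may exist there.

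**Conclusion.** The point holds in a limited form. SAP 8.4 is wrong to say that pattern mixture models identify data as MAR or MNAR, and wrong to plan the handling of missing scores from such a classification. That conclusion needs no numerical assumption.

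If the usual comparison by dropout pattern is what is meant, it can flag MAR dropout under which the mixed model is unbiased. It can also miss MNAR dropout that makes the mean change about 2 to 6 points too favourable on a QLQ-C30 scale. Those sizes depend on the assumed inputs (30% or 60% dropout, a 10-point unseen fall or log-odds of 0.7 per SD), and some MNAR mechanisms would be detected. The effect is confined to quality-of-life conclusions; the safety, survival and response analyses are untouched.

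**What to change.** In SAP 8.4:
- Delete the step that selects the handling from a data-based MAR/MCAR/MNAR classification, and the clause that pattern mixture models identify MAR or MNAR.
- State that, if the longitudinal model of protocol 8.4.6 is fitted, it is reported as the MAR analysis whatever the observed dropout patterns. The model can stay optional.
- Use the pattern mixture model, to which the SAP is already committed, as a sensitivity analysis. Worsen the post-dropout means of patients still alive by fixed deltas, for example 0, 5, 10 and 15 points on QLQ-C30 scales (downward for function and global health, upward for symptoms) and 0, 0.04, 0.08 and 0.12 on the EQ-5D-3L index. These ranges include the SAP's own important differences of 10 points (7.8.1) and 0.08 (4.3.3.2).
- Replace the undefined worst case and similarity rule with the delta at which the conclusion against 10 points (or 0.08) changes. With MAR mean change M and proportion π dropped out while alive, a functional-scale mean crosses -10 at delta = (M + 10)/π.
- Apply the deltas to the pattern-specific means. Otherwise amend the sentence that bars imputation after scoring so that it exempts this analysis.

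The cost is SAP wording and one added sensitivity analysis on data already collected. The quality-of-life result could also no longer be called MAR, or robust, on the strength of a test.

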9 CONTENT OF REPORTS

Study reports will be written corresponding to the final analyses of OS. The table, figure and listing outputs that will be produced will be described in the Data Presentation Plan for the study.

APPENDIX 1 SELECT ADVERSE EVENTS DEFINITION AND CONVENTIONS

The select Adverse Events (select AEs) consist of a list of preferred terms grouped by specific category (e.g. pulmonary events, gastrointestinal events categories) and by subcategory (e.g. pituitary disorders, diabetes, thyroid disorders, adrenal disorders subcategories). These categories and subcategories are defined by the Sponsor and the list that is most current at the time of analysis will be used. Also, changes may be made to this list with each new version of MedDRA.

For information, the select adverse events defined at the time of finalization of the first version of the document are listed in [Table 5](#) using MedDRA version 18.1. The final list used for the clinical study report will be included in an Appendix of the CSR.

Time-to onset definition

Time-to onset of select AE (any grade) for a specific category (i.e. pulmonary events, gastrointestinal events, endocrine adverse event, hepatic adverse event, hypersensitivity/infusion reaction, renal adverse event, skin adverse event) is defined as the time between the day of the first dose of study treatment and the onset date of the earliest select AE (of any grade) in this category.

If the subject did not experience a select AE (of any grade) in the category, time-to onset will be censored at the maximum follow-up time of all subjects in their respective treatment group (i.e. for subjects without an event, follow-up time is defined from first dosing date up to last dosing date +30 days (or 100 days depending on the analysis) if subjects are off treatment and followed for at least 30 days (or 100 days depending on the analysis) , otherwise it is defined up to the last known alive date). The resulting Kaplan-Meier plot will represent the cumulative rate of the select AE (any grade) in the category over time.

Time-to onset of select AE (grade 3-5) for a specific category is defined similarly but restricted to grade 3-5 select AEs.

Time-to onset of drug-related (grade 3-5 or any grade) select AE for a specific category is defined similarly but restricted to drug-related select AEs.

Time-to onset for a specific subcategory is defined similarly but restricted to event of this subcategory.

Time-to resolution definition

In order to derive the time-to resolution, overlapping or contiguous select AEs within a specific category (defined in [Table 5](#)) will be collapsed into what will be termed “clustered” select AEs. For example, if a subject (without pre-treatment AE) experienced an AE from 1st to 5th January, another AE (with different PT but within same category) from 6th to 11th January and same AE from 10th to 12th January, these will be collapsed into one clustered select AE from 1st to 12th January. [Table 4](#) is summarizing key derivation steps for each type of clustered select AEs.

Time-to resolution of select AE (any grade) for a specific category is defined as the longest time from onset to complete resolution or improvement to the grade at baseline among all clustered select AEs in this category experienced by the subject. Events which worsened into grade 5 events (death) or have a resolution date equal to the date of death are considered unresolved. If a clustered select AE is considered as unresolved, the resolution date will be censored to the last known date alive. Improvement to the grade at baseline implies that all different AE events in the clustered

select adverse event should at least have improved to the corresponding (i.e with same preferred term) baseline grade. This measure is defined only for subjects who experienced at least one select AE in the specific category.

The time-to resolution of select AE (grade 3-5) for a specific category is defined similarly with an onset date corresponding to a grade 3-5 select AE.

Time-to resolution of drug-related select AE (any grade or grade 3-5) is defined similarly but restricted to drug-related select AE.

The time-to resolution of select AE (any grade or grade 3-5, drug-related or all) where immune modulating medication was initiated is defined similarly with the additional condition that the subject started an immune modulating medication during the longest select AE resolution period.

Time-to resolution for a specific subcategory is defined similarly but restricted to event of this subcategory.

Table 4: Derivation of Clustered Select AE

Type of clustered select AE	Derivation
Any grade	
 • Collapse any on-treatment select AE from the same category
Drug-related of any grade	
 • Collapse any on-treatment drug-related select AE from the same category
Grade 3-5	
 • Collapse any on-treatment select AE from the same category. • Resolution will be based on the onset date of the earliest grade 3-5 records (if no grade 3-5 record, clustered select AE is excluded)
Drug-related of Grade 3-5	
 • Collapse any on-treatment drug-related select AE from the same category • Resolution will be based on the onset date of the earliest grade 3-5 record (if no Grade 3-5 record, clustered select AE is excluded)

The algorithm for collapsing select adverse event records is using the following conventions:

For each subject and specified category, the corresponding adverse event records will be collapsed when:

- 1) Multiple adverse event records have the same onset date.
- 2) The onset date of an event record is either the same day or 1 day later than the resolution date of a preceding event record (contiguous events).
- 3) The onset date of an event record is after the onset date and prior to or on the resolution date of a preceding event record (overlapping events).

Table 5: Select Adverse Events

Category	Subcategory	Preferred Term
ENDOCRINE ADVERSE EVENT	ADRENAL DISORDER	ADRENAL INSUFFICIENCY
		ADRENAL SUPPRESSION
		ADRENOCORTICAL INSUFFICIENCY ACUTE
		BLOOD CORTICOTROPHIN DECREASED
		BLOOD CORTICOTROPHIN INCREASED
		HYPOTHALAMIC PITUITARY ADRENAL AXIS SUPPRESSION
		SECONDARY ADRENOCORTICAL INSUFFICIENCY
	DIABETES	DIABETES MELLITUS
		DIABETIC KETOACIDOSIS
		FULMINANT TYPE 1 DIABETES MELLITUS
		LATENT AUTOIMMUNE DIABETES IN ADULTS
		TYPE 1 DIABETES MELLITUS
	PITUITARY DISORDER	HYPOPHYSITIS
		HYPOPITUITARISM
		LYMPHOCYTIC HYPOPHYSITIS
	THYROID DISORDER	ATROPHIC THYROIDITIS
		AUTOIMMUNE HYPOTHYROIDISM
		AUTOIMMUNE THYROIDITIS
		BASEDOW'S DISEASE
		BLOOD THYROID STIMULATING HORMONE DECREASED
		BLOOD THYROID STIMULATING HORMONE INCREASED
		HYPERTHYROIDISM
		HYPOTHYROIDISM

Table 5: Select Adverse Events

Category	Subcategory	Preferred Term
		PRIMARY HYPERTHYROIDISM
		PRIMARY HYPOTHYROIDISM
		THYROID FUNCTION TEST ABNORMAL
		THYROID HORMONES DECREASED
		THYROID HORMONES INCREASED
		THYROIDITIS
		THYROIDITIS ACUTE
		THYROXINE DECREASED
		THYROXINE FREE DECREASED
		THYROXINE FREE INCREASED
		THYROXINE INCREASED
		TRI-IODOTHYRONINE UPTAKE INCREASED
GASTROINTESTINAL ADVERSE EVENT		AUTOIMMUNE COLITIS
		COLITIS
		COLITIS ULCERATIVE
		DIARRHOEA
		ENTERITIS
		ENTEROCOLITIS
		FREQUENT BOWEL MOVEMENTS
		GASTROINTESTINAL PERFORATION
HEPATIC ADVERSE EVENT		ACUTE HEPATIC FAILURE
		ACUTE ON CHRONIC LIVER FAILURE
		ALANINE AMINOTRANSFERASE INCREASED

Table 5: Select Adverse Events

Category	Subcategory	Preferred Term
		ASPARTATE AMINOTRANSFERASE INCREASED
		AUTOIMMUNE HEPATITIS
		BILIRUBIN CONJUGATED INCREASED
		BLOOD ALKALINE PHOSPHATASE INCREASED
		BLOOD BILIRUBIN INCREASED
		DRUG-INDUCED LIVER INJURY
		GAMMA-GLUTAMYLTRANSFERASE INCREASED
		HEPATIC ENZYME INCREASED
		HEPATIC FAILURE
		HEPATITIS
		HEPATITIS ACUTE
		HEPATOTOXICITY
		HYPERBILIRUBINAEMIA
		LIVER DISORDER
		LIVER FUNCTION TEST ABNORMAL
		LIVER FUNCTION TEST INCREASED
		LIVER INJURY
		TRANSAMINASES INCREASED
HYPERSENSITIVITY/INFUSION REACTION		ANAPHYLACTIC REACTION
		ANAPHYLACTIC SHOCK
		BRONCHOSPASM
		HYPERSENSITIVITY
		INFUSION RELATED REACTION

Table 5: Select Adverse Events

Category	Subcategory	Preferred Term
PULMONARY ADVERSE EVENT		ACUTE RESPIRATORY DISTRESS SYNDROME
		ACUTE RESPIRATORY FAILURE
		INTERSTITIAL LUNG DISEASE
		LUNG INFILTRATION
		PNEUMONITIS
RENAL ADVERSE EVENT		ACUTE KIDNEY INJURY
		AUTOIMMUNE NEPHRITIS
		BLOOD CREATININE INCREASED
		BLOOD UREA INCREASED
		CREATININE RENAL CLEARANCE DECREASED
		HYPERCREATININAEMIA
		NEPHRITIS
		NEPHRITIS ALLERGIC
		PARANEOPLASTIC GLOMERULONEPHRITIS
		RENAL FAILURE
		RENAL TUBULAR NECROSIS
		TUBULOINTERSTITIAL NEPHRITIS
		URINE OUTPUT DECREASED
SKIN ADVERSE EVENT		AUTOIMMUNE DERMATITIS
		BLISTER
		DERMATITIS
		DERMATITIS ALLERGIC
		DERMATITIS EXFOLIATIVE

Table 5: Select Adverse Events

Category	Subcategory	Preferred Term
		DRUG ERUPTION
		ECZEMA
		ERYTHEMA
		ERYTHEMA MULTIFORME
		EXFOLIATIVE RASH
		FIXED DRUG ERUPTION
		NODULAR RASH
		PALMAR-PLANTAR ERYTHRODYSAESTHESIA SYNDROME
		PHOTOSENSITIVITY REACTION
		PRURITUS
		PRURITUS ALLERGIC
		PRURITUS GENERALISED
		PSORIASIS
		RASH
		RASH ERYTHEMATOUS
		RASH GENERALISED
		RASH MACULAR
		RASH MACULO-PAPULAR
		RASH MORBILLIFORM
		RASH PAPULAR
		RASH PRURITIC
		RASH VESICULAR
		SKIN EXFOLIATION

Table 5: Select Adverse Events

Category	Subcategory	Preferred Term
		SKIN HYPOPIGMENTATION
		SKIN IRRITATION
		STEVENS-JOHNSON SYNDROME
		TOXIC EPIDERMAL NECROLYSIS
		TOXIC SKIN ERUPTION
		URTICARIA
		VITILIGO

Source: MedDRA version 18.1

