7.5.3	Subgroups Analyses	23
7.6	Safety	24
7.6.1	Primary Analysis	24
7.6.1.1	High-grade (CTCAE v4.0 Grade 3 or higher) Treatment-Related, Select Adverse Events	24
7.6.2	Secondary Analysis	24
7.6.2.1	High-grade (CTCAE v4.0 Grade 3 or higher) Select Adverse Events	24
7.6.2.2	Select Adverse Events	24
7.6.3	Other Safety Analysis	24
7.6.4	Immunogenicity Analysis	25
	[REDACTED]	
7.8	Outcomes Research Analyses	25
7.8.1	EORTC QLQ-C30	25
7.8.2	EuroQoL Five Dimensions Questionnaire	26
8	CONVENTIONS.....	26
8.1	Baseline.....	26
8.2	Duration, On-study Event calculations.....	26
8.3	Conventions for Partial/Missing Dates.....	27
8.4	Missing Data	28
9	CONTENT OF REPORTS	28
APPENDIX 1	SELECT ADVERSE EVENTS DEFINITION AND CONVENTIONS.....	29
DOCUMENT HISTORY	37
REFERENCES	37	

LIST OF TABLES

Table 1:	Subject Cohorts	7
Table 2:	Protocol Amendments	9
Table 3:	Time Windows for Assessments.....	15
Table 4:	Derivation of Clustered Select AE	30
Table 5:	Select Adverse Events	31
Table 6:	Document History	37

LIST OF FIGURES

Figure 1:	Study Design Schematic	8
-----------	------------------------------	---

Research Hypothesis:

High-grade (CTCAE v4.0 Grade 3 or higher), treatment-related, select adverse events occur with a low frequency in subjects with histologically confirmed stage III (unresectable) or stage IV melanoma treated and progression after prior treatment containing an anti-CTLA-4 monoclonal antibody with nivolumab monotherapy.

Schedule of Analyses:

Several interim analysis will be conducted ad-hoc and as necessary to address queries from regulatory authorities.

The Scientific Steering Committee (SSC) will closely review the safety data throughout the study to evaluate the risk/benefit ratio in general and for the separate prospective subgroups following a predefined Safety Management Plan.

The final analysis will be conducted only after subjects who have met the screening criteria have been treated for a maximum of 24 months with safety follow-up at 30 [± 7] and 70-84 [± 7] days from first follow-up visit post-treatment.

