7 STATISTICAL ANALYSES

7.1 General Methods

In the analysis described below (except where noted), counts and percentages will be reported for discrete variables with inclusion of unknown or missing values as a separate category. The mean, standard deviation, median, range (minimum and maximum), and number of non-missing values will be reported for each continuous measure.

Adverse events and medical history will be coded according to the most recent Medical Dictionary for Regulatory Activities (MedDRA). Previous and [REDACTED] will be coded using the WHO Drug Dictionary.

The time to event distribution (i.e. overall survival) will be estimated using Kaplan Meier techniques. Median for time to event endpoints along with 95% confidence interval (CI) will be constructed based on 95% CI using the Brookmeyer and Crowley¹ method. Overall survival rates at selected time points, including survival rates at Years 1 and 2, together with their 95% CIs will also be estimated using KM estimates on the OS curves. Associated 2-sided 95% CIs will be calculated using the Greenwood formula.

All data summaries, unless otherwise noted, will be presented by subpopulations. A total column will be included in each summary.

- Mucosal
- Cutaneous
- Ocular/Uveal
- Acral
- Other
- ECOG PS2
- CNS Metastasis
- Autoimmune disease
- Grade 3-4 irAEs with anti-CTLA-4

Tables that will be presented by baseline LDH, BRAF mutation and type of autoimmune disorder should have the following presentation order:

- Baseline LDH: \leq ULN, $>$ ULN, and $> 2*ULN$
- BRAF status: Mutant, Wildtype, and Not reported, if no BRAF genetic mutation results are available.
- Type of autoimmune disorder: Endocrine, Gastrointestinal, Hepatic, Skin, and Other

Further, general methods information for the safety analysis, including general methods for adverse events and laboratory tests can be found in Section 7.1 of the CA209 Core Safety SAP version 4. Statistical analyses will be carried out using SAS software (SAS Institute, Cary, North Carolina, USA), unless otherwise noted.

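### Time to resolution censors patients who die with a select AE still open; if summarised by Kaplan-Meier, the share resolved is too high and the median too short

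*SAP*

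**What the plan says.** **Resolution.** SAP Appendix 1 measures the longest time from onset to complete resolution, or return to baseline grade, among a subject's clustered events in a category. On death it states: "Events which worsened into grade 5 events (death) or have a resolution date equal to the date of death are considered unresolved". It continues: "If a clustered select AE is considered as unresolved, the resolution date will be censored to the last known date alive". For the high-grade summaries, Table 4 of the same appendix states: "Resolution will be based on the onset date of the earliest grade 3-5 records". The endpoint itself, in Protocol 8.3.2 and SAP 4.2, is a median labelled Grades 3-4.

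**Estimator.** Appendix 1 names none for resolution. SAP 7.1 says: "The time to event distribution (i.e. overall survival) will be estimated using Kaplan Meier techniques". It then plans medians with Brookmeyer-Crowley intervals for time-to-event endpoints. SAP 7.6.2.2 refers both onset and resolution to Section 7.6.6 of the Core Safety SAP, which is not among the documents.

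**Onset.** For event-free subjects, Appendix 1 says that "time-to onset will be censored at the maximum follow-up time of all subjects in their respective treatment group". A bracket opened by *i.e.* adds that "follow-up time is defined from first dosing date up to last dosing date +30 days (or 100 days depending on the analysis", with the last known alive date as fallback. The stated aim follows: "The resulting Kaplan-Meier plot will represent the cumulative rate of the select AE (any grade) in the category over time".

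**The concern.** A secondary objective is to characterise the outcome of all high-grade select AEs, whether or not drug-related. Dying with the event open is one of those outcomes. Censoring it removes the patient from the risk set on the assumption that later recovery was as likely as for those still under observation. For an event that itself turned fatal, that assumption fails by construction. A Kaplan-Meier curve then estimates resolution in a setting without death, not the share of patients who recovered, and it errs in the favourable direction.

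The mismatch between Grades 3-4 and grade 3-5 also leaves unclear whether fatal events belong in the resolution set.

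The onset sentence raises a smaller question. If the bracket were taken as each subject's own censoring date, a programmer would draw a different curve from the one that the main clause describes.

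**Working it through.** The plan states no figure for onset or resolution, so there is nothing to reproduce. The checks below establish direction and size.

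**1. Direction, by a small example.** Take 10 events. Six resolve at months 1, 2, 3, 4, 5 and 6, and four patients die with the event open at months 1.5, 2.5, 3.5 and 4.5. The numbers at risk at the six resolutions are 10, 8, 6, 4, 2 and 1.
- Kaplan-Meier unresolved: 9/10 × 7/8 × 5/6 × 3/4 × 1/2 × 0 = 0, so 100% appear resolved at month 6. The observed share is 60%.
- The Kaplan-Meier median is month 4 (50.8% resolved). Half of the ten had actually resolved at month 5.

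**2. Size, with constant hazards.** Inputs:
- Median OS 16.8 months (95% CI 12.5 to 31.6), from CA209003 in Protocol 1.4.1. This is a different study. 16.8 × 30.4375 / 7 = 73.05 weeks.
- Kaplan-Meier median resolution m of 4, 13 or 26 weeks. These are assumptions; the documents give no resolution times.

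Formulas: hr = ln2/m; hd = ln2/73.05 = 0.00949 per week; L = hr + hd; share dying unresolved p = hd/L. Kaplan-Meier share resolved = 1 − exp(−hr·t). Share with death competing = (1 − p)(1 − exp(−L·t)), with median −ln(1 − 0.5/(1 − p))/L.

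For m = 4: hr = 0.17329, L = 0.18278, p = 5.2%. At 12 weeks, Kaplan-Meier gives 87.5%, against 0.948 × (1 − exp(−2.193)) = 84.2%.

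| Assumed KM median (weeks) | p (range over the OS interval) | Median, death competing (weeks) | Share resolved, KM vs death competing |
|---|---|---|---|
| 4 | 5.2% (2.8–6.9) | 4.10 | 87.5 vs 84.2% at 12 weeks |
| 13 | 15.1% (8.6–19.3) | 14.16 | 93.8 vs 81.7% at 52 weeks |
| 26 | 26.2% (15.9–32.4) | 31.35 | 75.0 vs 62.5% at 52 weeks |

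**3. Size, fixing the share that dies unresolved.** Patients with an open high-grade event may die faster than the whole population, so p can be set directly. Assume a median of 4 weeks to resolution or death (L = ln2/4). Then p = 5% gives 86.1 vs 83.1% at 12 weeks and medians of 4.21 vs 4.31 weeks. With p = 20%, the results are 81.1 vs 70.0% and 5.00 vs 5.66 weeks.

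**4. Onset, group-maximum reading.** If every event-free subject is censored at the group maximum, nobody leaves the risk set before the last event except by having one. So 1 − KM equals events divided by n exactly. In a simulation of 400,000 subjects (assumed event hazard 0.8% per month, median treatment 5 months, OS 16.8 months, 100-day window, complete follow-up), the 12-month rate is 5.35% under the group-maximum rule. It is also 5.35% with death and window end as competing events. Own-window censoring gives 9.23%. With an assumed 1% per month loss to follow-up, the group-maximum rule gives 5.13% against 5.35%.

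**The case against.** **The estimator for resolution is inferred.** SAP 7.1 illustrates time-to-event data with overall survival only, and the Core Safety SAP may specify something else. This stands, and the conclusion is conditional on it. Censoring plus a planned median makes Kaplan-Meier the natural choice but does not prove it.

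**The effect may be negligible.** For events that resolve within weeks the median barely moves (4.0 to 4.1 weeks). The shares at 12 and 52 weeks are not outputs that the SAP names. Protocol 1.4.3 reports that all drug-related Grade 3-4 select AEs on nivolumab in CA209037 resolved, which would mean no bias for that subset. This also stands. However, the objective covers all high-grade select AEs, and slow or absent recovery is foreseen: Protocol 3.6 provides for events deemed irreversible, and Table 5 lists type 1 diabetes and hypopituitarism.

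**The plan does not count death as recovery.** Correct. The problem is what censoring does afterwards, not the classification.

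**A stronger reading of the onset sentence is tempting:** that it contains two contradictory rules and could inflate onset rates about twofold. The documents do not support this. The bracket defines follow-up time, the term just used, and the group maximum is then taken over it. On an own-window reading, the words about the maximum of all subjects would do no work. The stated cumulative-rate aim fits the nested reading. Follow-up should also be largely complete, since the SAP's Schedule of Analyses says: "The final analysis will be conducted only after subjects who have met the screening criteria have been treated for a maximum of 24 months". At an assumed 5% incidence, even the own-window curve reaches only about 20% at 24 months (20.5% with median follow-up of 4 months), so a Kaplan-Meier median would not be reached under either reading.

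**Conclusion.** The resolution point holds conditionally. If Kaplan-Meier is used and someone dies with an event open before the last observed resolution, the share resolved is too high. The median is too short if such deaths come early enough to affect it. In the illustrations of step 2 the median is short by 0.1, 1.2 or 5.3 weeks, and the share resolved is too high by 3.3 points at 12 weeks or 12.1 to 12.5 points at 52 weeks. These sizes rest on constant hazards, on survival borrowed from another study and on assumed resolution times. The bias is nil without deaths during an open event.

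A reader might infer that the reported resolution times will certainly be misleading, or that the main safety result is compromised. Neither follows. The estimator is unconfirmed, the effect is small for events that resolve quickly, and the primary endpoint is a crude percentage that this rule does not touch. The grade mismatch is a labelling inconsistency, since Appendix 1 does say how Grade 5 is handled. The onset sentence needs clarification, not a change of method. Overall this is a cheap improvement to a secondary safety summary.

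**What to change.** - **Resolution (SAP Appendix 1):** treat death with an open event as a competing event and estimate cumulative incidence of resolution. Keep censoring for subjects alive with the event ongoing. Per category, report the numbers resolved, died unresolved and ongoing; these counts make the result interpretable under any estimator. Name the estimator.
- **Grade set:** make the Grades 3-4 label in Protocol 8.3.2 and SAP 4.2 agree with the grade 3-5 derivation in Appendix 1 and its Table 4, stating whether fatal events are included.
- **Onset:** reword the sentence to confirm that the bracket defines the follow-up over which the group maximum is taken.
- Check all three against Core Safety SAP 7.6.6 before editing.

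The cost is a few sentences, a standard competing-risks option and one extra output. Resolution figures may become slightly less favourable. The programme-standard output can be kept alongside for comparison with other nivolumab studies.
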